Secondary

To determine the effectiveness of 6 months closed-loop compared with manually determined insulin dosing on glucose control, psychosocial well-being, sleep, cognitive functioning, ECG and health economics measures in adults with type 1 diabetes.

Section 3: Study Methods

Trial design

HCL-Adult is a multicentre, open label, parallel-group, superiority randomized clinical trial with equally sized treatment groups.

The intervention will last for 26 weeks, with an additional minimum 5 week period of active run-in which includes education (pre-randomisation). The exact duration of run-in will depend on individual training requirements. The study flow is presented in Figure 1.

Randomization

Group allocation (HCL or continuing standard care) will be random with a 1:1 ratio using minimization with 3 stratification variables, all of which are expected to be highly prognostic of primary outcome. These minimization variables are: 1) % time in target range pre-randomisation (dichotomised into <= 55% and > 55%); 2) study centre (7 sites); and 3) insulin delivery modality at enrolment (MDI or IPT). Due to the nature of the intervention, blinding of participants and investigators is not possible.

Sample size

Sample size calculation is based on a parallel design with 2 equally sized groups.

Assumptions used were derived from JDRF CGM randomized clinical trials [8, 9] that recruited a sample of 69 adults (25-70 years old) with type 1 diabetes and a baseline HbA1C < 10.5%, 86% of whom were using IPT and 14% using MDI. All participants had masked CGM data at randomization and at 6 months. Study investigator [name], personal communication, provided estimates of the effective standard deviation of percentage time spent in target glycaemic range at 6 months (adjusted for baseline) which was 9% (95% CI 8% to 12%) for pump users and 10% (95% CI 7% to 19%) for MDI users.

To detect a difference in percentage time in target glycaemic range of 5% with 80% power and 5% type I error rate assuming a common standard deviation of 9%, a total of 104 participants are needed. Allowing a drop-out rate of 10% a total of 120 people will be recruited, 60 randomized to HCL while 60 randomized to control group.

A more conservative scenario with a dropout rate of 20%, and unequal SDs of 12% and 19% for IPT and MDI users, respectively, increases the minimum detectable absolute difference to 9% with a power of 80%.

Framework

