This study is a superiority study with all analysis being performed on this basis.

Statistical interim analyses and stopping guidance

No interim analysis is planned. The study device has been previously proven to be safe for people with type 1 diabetes [10]; therefore, early stopping due to safety issues is not expected. However, safety recommendations will be made by an independent Data Safety Monitoring Committee (DSMC).

Timing of final analysis

The primary outcome and secondary glucose outcomes will be analysed collectively at the conclusion of the study. Other secondary outcomes will be analysed separately at the end of the study.

Health economic outcome and biomarkers will be analysed at a later date after additional funding is obtained.

Timing of outcome assessments

Pre-randomisation outcomes are collected at Visits 3-6, mid-study outcomes are collected at Visits 9-11 and end-of-study outcomes are collected at Visits 12-15 (Figure 1)

[figure not shown]

Figure 1: Study flow and timing of outcome assessments

Section 4: Statistical principles

Confidence intervals and p values

All hypothesis testing will be two-sided with an α of 0.05, with reported 95% confidence intervals.

No corrections for multiplicity are planned to control Type I error; rather, the effectiveness of the intervention will be assessed based on the clearly specified primary outcome; secondary outcomes are exploratory in nature and will be labelled as such in publications arising from the study. A transparent approach to reporting results will be taken, with the list of all pre-specified secondary outcomes included in every publication resulting from this study (this list would include a reference to relevant publication if results already published).

Results will be interpreted in light of the number of comparisons and where multiple comparisons indicate multiple effects, the consistency of these results will be discussed.

Adherence and protocol deviation

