The primary analysis for this study will take an intention-to-treat approach; data from all participants will be analysed. Overall adherence to intervention in this setting is difficult to assess as it is composed of participant's adherence as well as system performance. CGM use will be used as a surrogate marker of participant's adherence to intervention – reported as the proportion of overall time that CGM was active with available glucose readings. This will be interpreted with caution as it will include technical issues beyond participant's control. HCL performance parameters (such as % time closed loop is active) are part of secondary analysis. These results will also be interpreted with caution as they are intertwined with participant's adherence.

No adherence parameters will be reported for the control population.

Protocol deviation was defined as a breach of Good Clinical Practice or the protocol that is likely to affect to a significant degree the safety or rights of a research participant or the reliability and robustness of the data generated in the research project.

The number and details of protocol deviations and violations will be presented as were reported by the study site.

Analysis populations

Entire study population

The entire study population is defined as all participants who were randomized (and have thus completed the run-in period of the first 6 visits of the study) regardless of their eligibility, deviations from protocol or adherence to intervention. Participants will be analysed according to the treatment arm to which they were randomised.

Complete case population(s)

The complete-case population is defined as all participants who were randomized to a treatment group for whom outcome data were available for analysis.

Note: given different patterns in missing data over different outcomes, the membership of each complete-case population differs based on the outcome being analysed.

Per protocol population

Per protocol population will exclude participants who:

- had the intervention (HCL) active for < 80% of the intervention period (auto-mode for less than 80% of time from randomisation to the end of the study due to either non-adherence to protocol or technical issues)
- standard treatment wearing real-time CGM (with or without alarms) at any time during the study
- wearing less than 3 or more than 5 masked CGM sensors at baseline and end of study

Safety population

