Section 6 Analysis

Primary outcome

Outcome definition

Primary outcome is the percentage of time spent in target glucose range (3.9-10 mmol/L) measured by masked CGM over 3 weeks starting at 23 weeks post randomization (\pm 3 weeks) (glucose measured at 5-min intervals). Participants with a low number of available CGM readings in one or more weeks will have the CGM repeated and may have up to 5 weeks of masked CGM collection. To accurately represent participant's glycaemic status, only days with at least 70% valid CGM readings will be used (>= 202 valid readings) [11]. The percentage of time spent in target glucose range will be calculated by dividing the number of sensor readings falling in the range 3.9 – 10 mmol/L by the total number of sensor readings and multiplying by 100 over the whole period of masked CGM collection. If the participant has less than 10 representative days [11] their outcome will be counted as missing (individual glucose values will not be imputed).

Analysis methods

To test for an effect of the treatment group on the primary outcome, an ANCOVA including treatment arm and baseline percent time in target range will be conducted. The primary outcome will be analysed on an intention-to-treat basis on the entire study population with missing outcome data imputed using multiple imputations under missing at random (MAR) assumption (overall time in range will be imputed rather than single glucose values, see section on Missing data).

Results will be presented as the mean difference in the percent time in target range between treatment arms at the end of the study with 95% confidence interval and p value.

Model residuals will be visually inspected to test the assumptions of the model. In the event of violations to homoscedasticity and non-normal distribution, the outcome will be transformed using a natural logarithm. If the ANCOVA model still displays poor fit, non-parametric analysis (Wilcoxon rank sum test) will be employed.

Sensitivity analyses

- 1. ANCOVA with adjustment for factors used in the minimisation will be conducted (study centre 7 categories, insulin delivery modality 2 categories).
- 2. Replication of primary outcome analysis in complete case population (missing completely at random (MCAR) assumption)
- 3. Replication of primary outcome analysis in full study sample using multiple imputation of missing data under missing not at random (MNAR) assumption (see section Missing data)

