- 4. Replication of primary outcome analysis in per-protocol population (see population definitions).

Planned subgroup/interaction analyses

The differential effect of the intervention on the primary outcome based on insulin regimen at enrolment (IPT or MDI) will be examined using a linear regression including terms for treatment group, regimen, a treatment group by regimen interaction, and baseline time in range.

Missing data

See Missing data section below.

Secondary outcomes

1. Glucose control

Outcome definition

Percent time in ranges (day/night/overall)

Percent time spent in the following ranges will be examined.

- 3.9 10.0 mmol/L
- < 2.8 mmol/L

- < 3.0 mmol/L*

- < 3.3 mmol/L

- < 3.9 mmol/L

- 3.9 7.8 mmol/L
- > 10.0 mmol/L
- > 13.9 mmol/L
- > 16.7 mmol/L

Percentage of time spent in each glucose range will be calculated by dividing the number of sensor readings falling in the range by the total number of valid sensor readings and multiplying by 100. This will be performed separately for day (6:00-23:59), night (00:00-5:59) and overall. Values will be calculated at baseline, mid-study, and end-of-study using masked CGM collection.

- Mean glucose level, standard deviation and coefficient of variation (SD/mean)

These metrics will be calculated using valid readings only, separately for day (6:00 - 23:59), night (00:00 - 5:59) and overall. Values will be calculated at baseline, mid-study, and end-of-study using masked CGM collection.

Fasting capillary blood glucose

Fasting capillary blood glucose is defined as the first capillary blood glucose taken between 5 am and 9 am during the period of masked CGM collection. These are recorded separately in blood glucose meters.

- HbA1c

HbA1c is measured from blood sample at enrolment, randomisation, mid-study (3 months post randomisation) and end-of-study (6 months post randomisation).

- 1.5-anhydrogluticol

This biomarker is measured at randomisation and end-of-study.

^{*}This outcome was not part of initial protocol, however it was added due to the position statement of the American Diabetes Association and the European Association for the Study of Diabetes published in 2017 ([12])

- Hypoglycaemic events

Events of symptomatic hypoglycaemia are defined as episodes of hypoglycaemia with glucose level < 3.5 mmol/L confirmed by a finger prick and requiring carbohydrate rescue. These events are self-reported and collected in participant's diary throughout the study.

Analysis method

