All secondary outcomes (except fasting capillary blood glucose and number of hypoglycaemic events) will be analysed using ANCOVA including treatment and baseline score of the outcome. Where the distribution of residuals is heteroscedastic even after logarithmic transformation, a Wilcoxon rank sum test will be performed (in which case no adjustments for baseline will be performed). With parametric methods, mean differences with 95% CI will be presented, whereas with non-parametric methods, median difference with 95% CI will be presented ([13]).

A mixed effects linear regression will be used to analyse fasting capillary blood glucose with random intercepts for individuals and study arm as a fixed effect.

The number of hypoglycaemic events will be analysed using Poisson regression or negative binomial regression if overdispersion is apparent.

Percent time in ranges, mean glucose, standard deviation and coefficient of variation will be performed separately for day (6:00 – 23:59) and night (0:00 – 5:59).

All analyses will be performed separately for mid-study and end-of-study data.

Sensitivity analysis

Due to exploratory nature of the outcomes, no sensitivity analysis will be performed.

Subgroup analysis

To estimate the effect of the intervention based on regimen (IPT or MDI), a treatment group by regimen interaction will be included in all models. Where non-parametric analysis will be performed, each regimen will be analysed separately.

2. Clinical outcomes

Outcome definition

- Change in average total daily dose of insulin and basal/bolus proportions taken over the last 7 days
- Change in insulin-to-carbohydrate ratio (ICR) (ICR is usually expressed in 1:X form where X represents grams of carbohydrates covered by 1 unit of insulin. This ratio can be constant throughout the day or can vary for breakfast, lunch and dinner times. It will be analysed separately for breakfast, lunch and dinner time, as well as a weighted average overall for the day)
- Change in body weight (kg)

All clinical outcomes are measured at randomisation, mid-study and end-of-study.

Analysis method

Linear regression will be used to evaluate the effect of treatment arm on the change score from baseline. Where the distribution of residuals is heteroscedastic even after logarithmic transformation, rank sum test will be performed.

All analysis will be performed separately for mid-study and end-of study.

Sensitivity analysis

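### The SAP splits a continuous diary count of hypoglycaemic events into mid-study and end-of-study analyses without counting dates, person-time or a stated whole-follow-up comparison

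*SAP*

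**What the plan says.** All references are to the SAP.

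- **Collection** (Section 6, Secondary outcomes, 1. Glucose control, Hypoglycaemic events). Symptomatic events confirmed by finger prick are counted. "These events are self-reported and collected in participant's diary throughout the study".
- **Model** (same section, Analysis method). "The number of hypoglycaemic events will be analysed using Poisson regression or negative binomial regression if overdispersion is apparent". This outcome is named as an exception to the baseline-adjusted ANCOVA used for most glucose outcomes. No offset, exposure time or baseline covariate is given. The subgroup paragraph implies treatment and regimen terms, because it puts their interaction in all models.
- **Split** (same section, Analysis method). "All analyses will be performed separately for mid-study and end-of-study data". No exception is made for the event count.
- **Meaning of the labels** (Section 3, Timing of outcome assessments). "mid-study outcomes are collected at Visits 9-11 and end-of-study outcomes are collected at Visits 12-15". Pre-randomisation outcomes are placed at Visits 3-6.
- **Follow-up** (Section 3, Trial design). "The intervention will last for 26 weeks, with an additional minimum 5 week period of active run-in". The entire study population is defined in Section 4 as randomised participants who "have thus completed the run-in period of the first 6 visits of the study".

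**The concern.** A mid-study/end-of-study split suits outcomes assessed at a time point, such as HbA1c or a masked CGM period. It does not suit a count that accumulates continuously. Applied with the SAP's visit definition, it would leave the weeks before Visit 9 and the gap between Visits 11 and 12 out of the only modelled comparison of symptomatic hypoglycaemic events.

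The objectives ask about 6 months of closed loop, so the natural quantity is the event rate over those 6 months. The trial is open label and the events are self-reported. If the counting period is not fixed in advance, it could be chosen after the data are seen. Without an exposure term, a participant who leaves early contributes a low count as if fully observed. The sample size section allows for 10% dropout, and for 20% in its conservative scenario.

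**Working it through.** The SAP gives no rate, dispersion or precision figure for this outcome, so there is no stated figure to reproduce. Its only design calculation, 104 participants for the primary outcome, plays no part here.

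**Step 1. Which visits fall in which analysis.** Randomisation follows the first 6 visits. Mid-study is Visits 9-11 and end of study is Visits 12-15. Visits 7 and 8, and the time between Visits 11 and 12, are in neither set.

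**Step 2. Share of follow-up covered.** Follow-up is 26 weeks. The end-of-study primary outcome is "measured by masked CGM over 3 weeks starting at 23 weeks post randomization", and participants with too few readings "may have up to 5 weeks of masked CGM collection". I take 3 to 5 weeks as the length of each window. The text does not give the mid-study length, so that part is an assumption.

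Share covered = (mid-study weeks + end-of-study weeks) / 26.

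| Reading | Weeks counted | Covered | In neither analysis |
|---|---|---|---|
| Windows of 3 and 3 weeks | 6 | 6/26 = 23% | 20 weeks, 77% |
| Windows of 3 and 5 weeks | 8 | 8/26 = 31% | 18 weeks, 69% |
| Windows of 5 and 5 weeks | 10 | 10/26 = 38% | 16 weeks, 62% |
| Successive intervals, 13 and 13 weeks | 26 | 26/26 = 100% | 0 |

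The 13-week intervals follow from the 3-month mid-study point that the SAP gives for HbA1c. A third reading, in which both counts are cumulative from randomisation, would make the end-of-study count the 6-month count. No text states it.

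**Step 3. Precision of one analysis against a full 26-week count.** For a negative binomial count with 60 per arm (the planned allocation), equal rates and complete follow-up:

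Var(log rate ratio) = (2/60) × (1/μ + k), where μ = weekly rate × weeks and k is the dispersion.

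Weekly rates of 0.2 and 1 and dispersions of 0.5 and 1.0 are assumptions; the SAP gives neither. The factor 2/60 cancels in the ratio of standard errors.

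| Rate, k | SE, 3 weeks | SE, 26 weeks | Ratio, 3 v 26 weeks | Ratio, 13 v 26 weeks |
|---|---|---|---|---|
| 0.2, 0.5 | 0.269 | 0.152 | 1.77 | 1.13 |
| 0.2, 1.0 | 0.298 | 0.199 | 1.50 | 1.08 |
| 1, 0.5 | 0.167 | 0.134 | 1.24 | 1.04 |
| 1, 1.0 | 0.211 | 0.186 | 1.13 | 1.02 |

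Example, first row: 3 weeks gives μ = 0.6 and 1/0.6 + 0.5 = 2.167; 26 weeks gives μ = 5.2 and 1/5.2 + 0.5 = 0.692; √(2.167/0.692) = 1.77. For 13 weeks, μ = 2.6 and 1/2.6 + 0.5 = 0.885; √(0.885/0.692) = 1.13.

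The cost in precision is thus 13% to 77% in the standard error with 3-week windows, and 2% to 13% with successive intervals.

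**The case against.** The strongest reply is that the SAP never confines diary events to Visits 9-11 or 12-15. The visit schedule is general, while the rule specific to this outcome is collection throughout the study. Where the glucose section wants a window it says so: the CGM metrics and fasting glucose are tied to masked CGM collection, and the event count is not. The split sentence is also loose. 1,5-anhydroglucitol is in the same section but is measured only at randomisation and end of study, so the sentence cannot apply literally to every outcome.

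This stands, and it rules out three stronger readings:

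- *That the plan discards the early weeks and most of follow-up.* This follows only under the window reading; the interval reading drops nothing.
- *That the missing weeks are when injection users first use a pump and closed loop.* The SAP text does not say when either starts and gives no dates for Visits 7-9. The figure showing the study flow is not available to check.
- *That the run-in count is barred from the model.* The SAP removes this outcome from ANCOVA and then states no baseline term. That is silence, not a prohibition.

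The reply does not remove the point. The visit definition is the only general one in the SAP, and the sleep measures use the labels as visit windows too. Where the authors meant the whole period, as for closed-loop performance, they said so. Successive intervals still give no single 6-month comparison, and only the unstated cumulative reading would supply one.

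It is also fair that the diary count is not the only view of hypoglycaemia. Severe hypoglycaemia is tabulated by arm under Safety without this split, and CGM time below 3.9, 3.3, 3.0 and 2.8 mmol/L is analysed. The safety table covers only episodes needing another person's help, however, and has no formal comparison.

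**Conclusion.** The point holds as a badly fixed analysis, of minor to moderate weight. The split is applied to a continuously collected count with no exception, and no counting dates, exposure offset or baseline term are stated. Under the SAP's own visit definition, 62% to 77% of the 26 weeks would be in neither analysis, assuming windows of 3 to 5 weeks. Under successive intervals the loss is nil, and what remains is the absence of one 6-month comparison and a small loss of precision per analysis. The precision figures depend on the assumed rates and dispersion.

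The weight is limited because secondary outcomes are declared exploratory and other hypoglycaemia measures are reported. The point does not touch the primary analysis.

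**What to change.** In Section 6, Secondary outcomes, 1. Glucose control, Analysis method:

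1. Exempt hypoglycaemic events from the mid-study/end-of-study split.
2. Make the main analysis one count per participant from randomisation to end of study or withdrawal, by Poisson or negative binomial regression, with log person-time as offset and with treatment arm and the run-in diary event rate as covariates.
3. Keep any mid-study and end-of-study counts as supplementary, and state the start and end date of each.
4. Tabulate events and person-time by arm for randomisation to Visit 9, so that early follow-up is visible.

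The cost is SAP wording. According to the SAP the diary already runs throughout the study, so no extra visits or participants are needed.

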Due to exploratory nature of the outcomes, no sensitivity analysis will be performed.

Subgroup analysis

To estimate the effect of the intervention based on regimen (IPT or MDI), a treatment group by regimen interaction will be included in all models. Where non-parametric analysis will be performed, each regimen will be analysed separately.

3. Psychosocial, sleep and cognitive functioning

Outcome definition

- Psychological wellbeing
 - Hypoglycaemia Fear Survey II short form (HFSII-SF)
 - Behaviour subscale (0 to 20)
 - Worry subscale (0 to 24)
 - Hypoglycaemia Avoidance Scale (HAS) (currently being validated, therefore scales might change)
 - Behaviour subscale (0 to 48)
 - Worry subscale (0 to 48)
 - Problem areas in diabetes (PAID)
 - Total (0 to 100)
 - Diabetes positive wellbeing (W-BQ28)
 - Total (0 to 12)
- Quality of life
 - DAWN impact of diabetes profile (DIDP)
 - Total (1 to 7 for each dimension; and for total score)
- Treatment satisfaction
 - Diabetes treatment satisfaction questionnaire (DTSQs)

Total (0 to 36)

Diabetes treatment satisfaction questionnaire (DTSQc)

Total (- 18 to +18.)

- Sleep quality
 - Pittsburgh sleep quality index (PSQI)
 - Total (0 to 21)
 - Psychomotor Vigilance Test (averaged over visits 3-4, 9-10 and 12-13)
 - Average reaction time
 - Total number of lapses (response times above 500 milliseconds)
 - Average of the fastest 10% and slowest 10% of responses
 - o Karolinska Sleepiness Scale (averaged over visits 3-5, 9-11 and 12-14)
 - Average Score 1 to 9
 - Actigraphy and sleep diary (averaged over visits 3-5, 9-11 and 12-14)

- Average sleep time
- Average sleep efficiency (time asleep / total time in bed)
- Average sleep onset latency
- Memory
 - Prospective-retrospective memory questionnaire (PRMQ)
 - Total (16 to 80)

Analysis method

All outcomes will be analysed using ANCOVA including intervention group and baseline outcome score. Model residuals will be visually assessed to ensure assumptions are met and a logarithmic transformation of the outcomes will be performed in the presence of heteroscedasticity or non-normally distributed outcomes. A non-parametric analysis will be used if model assumptions are violated. The mean difference in outcomes with 95% confidence intervals will be presented for parametric analyses and the median difference in outcomes with 95% confidence intervals for non-parametric analyses.

Sensitivity analysis

No sensitivity analysis will be performed.

Subgroup analysis

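### Insulin dose, carbohydrate ratio and weight are analysed as change scores without the available baseline value, and the log step before the rank sum test is undefined for outcomes that can be zero or negative

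*SAP*

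**What the plan says.** SAP Section 6, Secondary outcomes, item 2 (Clinical outcomes) defines each outcome as a change. The first is "Change in average total daily dose of insulin and basal/bolus proportions taken over the last 7 days"; the others are change in ICR (by meal and as a daily weighted average) and change in body weight. On timing it says: "All clinical outcomes are measured at randomisation, mid-study and end-of-study". The model is given in one sentence, "Linear regression will be used to evaluate the effect of treatment arm on the change score from baseline", and the fallback in the next: "Where the distribution of residuals is heteroscedastic even after logarithmic transformation, rank sum test will be performed". It gives no baseline covariate, offset or log-ratio, and does not say which quantity is logged.

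The rest of Section 6 mostly adjusts for baseline:

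- The primary outcome uses ANCOVA with baseline time in range.
- The glucose outcomes use ANCOVA with the baseline score, except fasting capillary glucose and hypoglycaemic event counts. Fasting glucose has a mixed model with "random intercepts for individuals and study arm as a fixed effect".
- For the psychosocial, sleep and cognitive outcomes: "All outcomes will be analysed using ANCOVA including intervention group and baseline outcome score".

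Where the SAP does say what is logged (the primary outcome, and the psychosocial, sleep and cognitive outcomes), it is the outcome itself.

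**The concern.** There are two separate problems in the same two sentences.

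First, the clinical outcomes are the one continuous group analysed purely as change, although the baseline is in hand. No reason is given. A change score in effect fixes the baseline slope at 1, whereas ANCOVA estimates it. When the true slope is below 1, the change score over-corrects, which adds noise and lets a chance baseline difference between arms leak into the estimate.

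Second, the sequence linear model, then log, then rank sum test has a middle step that cannot be carried out on a signed change. Anyone whose weight, dose or ICR is unchanged or lower has no logarithm. The rank sum test is triggered by what the residuals look like after that step, so the decision rule is not defined as worded. The analyst would have to decide what to do after seeing the data. The same rule is applied to other outcomes whose printed range or nature includes zero or negative values.

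**Working it through.** **Inputs.** From the SAP: two arms of 60 and 10% dropout, so 120 × 0.9 = 108 completers, 54 per arm. The SAP gives no SD, baseline-to-follow-up correlation r or expected mean change for the clinical outcomes, so r and the mean change are assumptions shown over a range.

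**The plan's own figure (context only).** The sole planning calculation is for the primary outcome: difference 5, SD 9, two-sided 5%, power 80%. The normal formula gives 51 per arm (102 in total); the noncentral t gives 52 per arm, which is the stated 104. Nothing below depends on it.

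**Precision.** Let σ be the SD at both times (assumed equal). The variance per participant that enters the treatment comparison is:

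- unadjusted change: 2σ²(1 − r)
- ANCOVA: σ²(1 − r²)
- ratio: 2(1 − r)/(1 − r²) = 2/(1 + r)

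**Chance imbalance.** With 60 per arm, the SE of the baseline difference is √(2/60) = 0.183 SD. Given an imbalance of d, the change-score estimate is shifted by (1 − r)d, in the direction opposite to the imbalance.

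| r (assumed) | Variance ratio 2/(1+r) | SE ratio | Shift for a 1-SE imbalance |
|---|---|---|---|
| 0.5 | 1.33 | 1.155 | 0.09 SD |
| 0.7 | 1.18 | 1.085 | 0.05 SD |
| 0.9 | 1.05 | 1.026 | 0.02 SD |
| 0.98 | 1.01 | 1.005 | 0.004 SD |

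A simulation with 54 per arm (4,000 runs for each r) gave SE ratios of 1.137, 1.083 and 1.020 at r = 0.5, 0.7 and 0.9, close to the formula. In terms of 108 completers, ANCOVA would reach the same precision with 108(1 + r)/2, that is about 27, 16 and 5 fewer participants at r = 0.5, 0.7 and 0.9.

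**The log step.** Evaluated numerically, log(−1) is not a number and log(0) is minus infinity. If changes were normal, the share at or below zero would be Φ(−mean/SD): 16% at a mean of +1 SD, 31% at +0.5 SD, 50% at 0 and 69% at −0.5 SD. The means are assumed; the figures only show that non-positive changes would be common under ordinary conditions.

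**Other outcomes under the same rule.** By the SAP's own ranges, PAID runs from 0 to 100 and DTSQc from −18 to +18. HFSII-SF, HAS, W-BQ28, DTSQs and PSQI also start at 0. The number of lapses and the percentage of time below 2.8 mmol/L can be zero.

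**The case against.** Change score versus ANCOVA is a choice of efficiency, not of validity. A reader might infer that the unadjusted change is biased, for example by regression to the mean. It is not: under randomisation regression to the mean acts equally on both arms in expectation. Minimisation on insulin delivery modality also limits imbalance on a factor plausibly related to dose and basal/bolus share. Where r is high, as it may be for weight, the loss is close to nil. All of this stands, and it limits the first problem to precision and chance imbalance.

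On the log step, it applies only if residuals look poor, and the clinical-outcomes text does not say that the difference is what gets logged. Logging positive raw values before differencing would be computable. That stands as an ambiguity, but the SAP does not write it, and where it is explicit it logs the outcome itself. A reader might also infer that software would silently drop participants and leave a comparison in half of the sample, selected on the outcome. The documents do not support that: they give no distribution of changes. In R, one of the named packages, the log of a negative value raises a warning and log(0) stops a linear model. An analyst may simply move to the rank sum test. What remains is that the step is undefined as worded.

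Two further inferences go too far. From its signed range a reader may conclude that DTSQc has no baseline score; the SAP says neither this nor when DTSQc is given, so only the log problem follows. And the SAP places fasting capillary glucose within masked CGM collection but, unlike the CGM metrics, does not list baseline explicitly, so a baseline value is likely but not stated.

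**Conclusion.** The point holds in limited form. The clinical outcomes omit an available baseline covariate for no stated reason. The cost is a standard error larger by about 15% at r = 0.5, 8% at 0.7, 2.6% at 0.9 and 0.5% at 0.98, assuming equal SDs at both times and with r itself assumed, plus exposure to chance imbalance. It is not a bias on average. The log step is undefined for zero or negative changes if applied to the outcome, as the SAP does elsewhere, and likewise for other outcomes that can be zero or negative; how many participants this would touch cannot be derived from the SAP.

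The SAP labels its secondary outcomes exploratory, and neither the primary result nor the sample size depends on them. There is also a wording conflict to reconcile: under Glucose control the SAP assigns ANCOVA with baseline to all secondary outcomes but two. Its placement suggests that it covers the glucose outcomes only, but read literally it contradicts the clinical-outcomes model.

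**What to change.** - **Clinical outcomes:** analyse the mid-study and end-of-study values by ANCOVA with treatment arm and the value at randomisation. Keep baseline in the models that add the treatment-by-regimen interaction.
- **Log step, positive measures:** if a log is needed, apply it to the positive follow-up and baseline values, not to their difference, and say so.
- **Outcomes that can be zero or negative:** omit the log step. Go directly to the stated non-parametric fallback, or pre-specify an alternative such as robust standard errors. The latter is one option among several; it keeps the baseline adjustment, which the SAP says is lost for the glucose outcomes under the rank sum test.
- **Fasting capillary glucose:** if it is recorded during the baseline masked CGM period, add each participant's baseline mean to the mixed model.
- **Scope:** limit the general ANCOVA sentence under Glucose control to the glucose outcomes.

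The cost is SAP wording only. The clinical outcomes are already measured at randomisation, so no new data are needed for them; the fasting-glucose change depends on the condition stated.
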